9.2.3 ANALYSIS POPULATION

9.2.3.1 SAFETY ANALYSIS POPULATION

The All Patients as Treated (APaT) population will be used for the analysis of safety data in this study. The APaT population consists of all enrolled subjects who received at least 1 dose of study treatment. At least one laboratory or vital sign measurement obtained subsequent to at least one dose of trial treatment is required for inclusion in the analysis of each specific parameter. To assess change from baseline, a baseline measurement is also required.

9.2.3.2 EFFICACY ANALYSIS POPULATION

The analysis of primary efficacy endpoints are based on the intention-to-treat (ITT) population, i.e., subjects will be included if they receive at least one dose of study medication.

9.2.4 STATISTICAL METHODS

9.2.4.1 STATISTICAL METHODS FOR TOLERABILITY ANALYSES

The trial will feature a two-stage minimax trial design (Simon 1989, A'hern, 2001) which tests for futility in a smaller sample of patients before proceeding with treatment of the full cohort. The accrual rate will be 1 patient/month in relapsed/refractory myeloid and B cell malignancies following allogeneic stem cell transplant to assess the safety and feasibility of pembrolizumab. The primary outcome is whether the patient remains DLT-free at the end of treatment. *A priori*, we expect 40% or fewer patients on an unsafe treatment would finish without experiencing a DLT, and at least 65% of patients would be DLT-free on a safe treatment. For $\alpha = 0.05$ and 80% power, we would need to observe

at least 5 DLT-free treatments out of a small sub-sample of 12 patients before we would consider evaluating pembrolizumab in the full sample of 26 patients. If at least 14 of the 26 patients respond remain DLT-free, we would have sufficient evidence to warrant further study of pembrolizumab in a future trial.

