A DLT is defined as the development of grade 3 or 4 acute GVHD (defined by the Gluckensberg scale), graft rejection, the development of any unexpected grade > 2 toxicity felt to be related to pembrolizumab, or the development of > grade 2 dysfunction of a vital organ felt to be secondary to an immune-related adverse event within 90 days following the initiation of pembrolizumab treatment. For immune-related adverse events that do not meet criteria for a DLT, but do meet criteria for a treatment-limiting toxicity (TLT), for example grade 2 acute GVHD, pembrolizumab will be held until the toxicity has

decreased to \leq grade 1. It will be permanently discontinued if delayed for >12 weeks. For patients who develop GVHD or an immune-related adverse event while on pembrolizumab, corticosteroid therapy and potentially other immunomodulatory agents will be initiated.

If the safety and feasibility of pembrolizumab is confirmed in this patient cohort, a phase II expansion cohort may be considered, particularly for disease subtypes where objective responses have been observed.

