8.2 ASSESSING AND RECORDING ADVERSE EVENTS

The rate of subject entry and expansion will depend upon assessment of the safety profile of patients entered at the previous dose level. Toxicity will be evaluated according to the NCI Common Terminology Criteria for Adverse Events (CTCAE), Version 4.0 (see Appendix E). If at least 5 of the first 12 patients complete pembrolizumab treatment without developing a DLT, we will open an expansion cohort to enroll with plans to enroll 14 additional patients should DLT-associated stopping rule not be met in the first 12 patients. If at least 14 of the 26 patients remain DLT-free, we would have sufficient

evidence to warrant further study of pembrolizumab in a future trial.

This particular safety stopping rule is based on the expected 50% rate of GVHD that has been reported to develop after DLI therapy³⁰. The inclusion of an expansion cohort will enable a further and more robust safety signal, as well as provide a larger cohort of patients in whom to assess clinical response, especially given the mixture of diseases that are being included in this study.

8.2.1 DEFINITION OF AN OVERDOSE FOR THIS PROTOCOL AND REPORTING OF OVERDOSE TO THE SPONSOR

For purposes of this trial, an overdose will be defined as any dose exceeding the prescribed dose for pembrolizumab will be defined as any dose of 1000 mg or greater. No specific information is available on the treatment of overdose of pembrolizumab. In the event of overdose, pembrolizumab should be discontinued and the subject should be observed closely for signs of toxicity. Appropriate supportive treatment should be provided if clinically indicated.

If an adverse event(s) is associated with (“results from”) the overdose of pembrolizumab, the adverse event(s) is reported as a serious adverse event, even if no other seriousness criteria are met.

If a dose of pembrolizumab according to the definition of overdose is administered without any associated clinical symptoms or abnormal laboratory results, the overdose is reported as a non-serious Event of Clinical Interest (ECI), using the terminology “accidental or intentional overdose without adverse effect.”

All reports of overdose with and without an adverse event must be reported within 24 hours to the sponsor either by electronic media or paper.

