8.4 TRIAL GOVERNANCE AND OVERSIGHT

8.4.1 DATA MONITORING COMMITTEE

The principal investigator will ensure that trial is conducted and data are generated,

documented, and reported in compliance with the protocol, accepted standards of Good Clinical Practice, and all applicable federal, state, and local laws, rules and regulations relating to the conduct of the clinical trial. The trial will specifically be evaluated by the principal investigator after the first 12 patients are enrolled to assess if the trial should be continued.

A quality assurance audit/inspection of this study may be conducted by regulatory authorities. The quality assurance auditor will have access to all medical records, the investigator's study-related files and correspondence, and the informed consent documentation of this clinical study.

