9.1.1 SAFETY ANALYSES

The study will initially enroll 12 patients in the first stage of the two-stage trial design. The accrual rate will be 1 patient/month in relapsed/refractory myeloid and B cell malignancies following allogeneic stem cell transplant to assess the safety and feasibility of pembrolizumab. If at least 5 of the first 12 patients complete pembrolizumab treatment without developing a DLT, we will open an expansion cohort to enroll with plans to enroll 14 additional patients should DLT-associated stopping rule not be met in the first 12 patients. Specifically, if 5 or more of the first 12 enrolled patients develop a DLT, including grade 3-4 GHVD, then the study will be halted. If at least 14 of the 26 patients remain DLT-free, we would have sufficient evidence to warrant further study of pembrolizumab in a future trial. Furthermore, if severe GVHD (grade 3-4) develops within the first 90 days of pembrolizumab treatment in each of the first 5 patients treated on the study (i.e. develop a DLT), it will be permanently closed to accrual as a measure to ensure safety.

Toxicity will be graded per the CTCAE guidelines and the maximally tolerated dose will be defined a less or equal than 1 in 6 patients with DLTs. All patients who receive any amount of the study drug will be evaluable for toxicity.

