9.1.3 INTERIM ANALYSIS

After the first 12 patients have been enrolled and have received at least 1 dose of pembrolizumab, an interim safety analysis will be performed. If < 5 of the first 12 patients develop a DLT (including grade 3-4 acute GVHD) following pembrolizumab treatment, an expansion cohort of 14 additional patients will be enrolled in order to obtain a more robust safety signal, as well as to enhance numbers of treated patients for efficacy analyses, given that patients with a wide variety of hematological malignancies will be enrolled. However, if ≥ 5 of the first 12 enrolled patients develop a DLT, then the study will be permanently closed to accrual. Furthermore, if severe GVHD (grade 3-4) develops in each of the first 5 patients treated on the study, it will be permanently closed to accrual as a measure to ensure safety.

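### The time frame of the primary DLT outcome differs between sections, and the stage-1 decision on the first 12 patients carries no minimum follow-up

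*Combined protocol and SAP*

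**What the plan says.** All references are to the combined protocol and SAP.

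**Time frame of a DLT**
- Section 2.1 lists four kinds of DLT, and the last ends "secondary to an immune-related adverse event within 90 days following the initiation of pembrolizumab treatment". The sentence does not show whether the 90 days governs all four or only the last.
- Section 9.1.1 has a separate closure rule if grade 3-4 GVHD "develops within the first 90 days of pembrolizumab treatment in each of the first 5 patients", and glosses this in brackets as developing a DLT. Section 9.1.3 repeats the rule without the 90 days.
- Section 9.2.4.1: "The primary outcome is whether the patient remains DLT-free at the end of treatment". Its design rates use the same time scale: "we expect 40% or fewer patients on an unsafe treatment would finish without experiencing a DLT", against at least 65% DLT-free on a safe one. Treatment runs for up to 24 months (2.1, 6.2.3).

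**Decision rules**
- Go rule (8.2, repeated in 9.1.1): "If at least 5 of the first 12 patients complete pembrolizumab treatment without developing a DLT, we will open an expansion cohort". Section 9.2.4.1 also asks for at least 5 of 12 DLT-free.
- Halt rule (9.1.1, restated in 9.1.3): "if 5 or more of the first 12 enrolled patients develop a DLT, including grade 3-4 GHVD, then the study will be halted". No time limit is given.
- Final rule (8.2, 9.1.1, 9.2.4.1): at least 14 of 26 DLT-free.

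**Timing of stage 1**
- Section 9.1.3: "After the first 12 patients have been enrolled and have received at least 1 dose of pembrolizumab, an interim safety analysis will be performed".
- Section 8.4.1: the trial is "evaluated by the principal investigator after the first 12 patients are enrolled to assess if the trial should be continued".

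No section states a minimum follow-up for the 12, a pause in accrual, or how to count a patient who leaves before the end of the window without a DLT.

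**The concern.** DLT-free status is the primary outcome, and the stage-1 count is the safety gate of a trial motivated by the risk of GVHD. The same patient should be counted the same way whichever section is consulted. Two kinds of patient may not be:

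- **Late event.** A qualifying toxicity after day 90 but during treatment is a failure under an end-of-treatment reading and not a DLT under a 90-day reading. This can move both the stage-1 count and the final count.
- **Early leaver without a DLT.** This patient ends treatment DLT-free (9.2.4.1) but has arguably not completed it (go rule in 8.2 and 9.1.1). This affects stage 1 only.

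Separately, a gate that may be decided when the twelfth patient has had one dose can be passed because DLTs have not yet had time to appear. The trial is open-label and the principal investigator makes the evaluation, so the counting rules should be fixed beforehand.

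**Working it through.** **Inputs.** First 12 patients; 1 patient/month (9.1.1, 9.2.4.1); unsafe DLT-free rate 40%, so DLT rate 60%; safe 65%, so 35% (9.2.4.1); 90 days (2.1, 9.1.1); 21-day cycles, 35 cycles (1.0, 2.2). Assumptions: decision when patient 12 receives dose 1, even spacing of 30.44 days, all DLTs within 90 days.

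**Plan's own figure.** An exact search for the two-stage minimax design (40% against 65%, alpha 0.05, power 80%) returns 12 and 26, as stated. The cut-offs it returns differ from those written; that is a separate matter and is not used here.

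**Follow-up at the earliest decision.** Patient *i* has (12 - *i*) x 30.44 days: 335 for patient 1, 91 for patient 9, then 61, 30 and 0. Nine of 12 have a full 90 days.

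**Completion.** Dose 17 is due 16 x 21 = 336 days after dose 1, and section 6.2.2 allows 3 days early, so patient 1 has had 16 or 17 doses. Dose 35 is due 34 x 21 = 714 days after dose 1. If completion means 35 cycles, nobody has completed. The fifth completer would come at 4 x 30.44 + 714 = day 836, about month 27, beyond the 10-20 month enrolment period in section 1.0.

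**DLTs visible, uniform onset, 60% rate.** Visible probability = 0.60 x min(days/90, 1).
- Patients 1-9: 0.60 each
- Patient 10: 0.60 x 60.88/90 = 0.406
- Patient 11: 0.60 x 30.44/90 = 0.203
- Patient 12: 0

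Expected visible: 5.40 + 0.406 + 0.203 = 6.01 of 7.20, so about 1.2 are unseen (about 0.7 at a 35% rate).

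**Chance of passing stage 1.** Let A be binomial(9, 0.60). Patients 10 and 11 show 0, 1 or 2 DLTs with probability 0.4735, 0.4441 and 0.0824.
- Fewer than 5 DLTs: 0.4735 x P(A<=4) + 0.4441 x P(A<=3) + 0.0824 x P(A<=2) = 0.4735 x 0.2666 + 0.4441 x 0.0994 + 0.0824 x 0.0250 = 0.172
- At least 5 DLT-free (at most 7 DLTs): 0.4735 x 0.9295 + 0.4441 x 0.7682 + 0.0824 x 0.5174 = 0.824

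| Unsafe treatment, 60% DLT rate | Fewer than 5 DLTs | At least 5 DLT-free |
|---|---|---|
| All 12 followed 90 days, binomial(12, 0.60) | 0.057 | 0.562 |
| Earliest decision, uniform onset | 0.172 | 0.824 |
| Only patient 12's DLT unseen, binomial(11, 0.60) | 0.099 | 0.704 |
| All DLTs at day 90, binomial(9, 0.60) | 0.267 | 0.930 |

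Under fewer than 5 DLTs with uniform onset, the figure is 0.12 at 0.5 patients/month and 0.20-0.22 at 1.2-1.3/month (12 in 10 months, 26 in 20 months).

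**Do the design rates carry over to 90 days?** Suppose all, three quarters or half of the 60% falls within 90 days. With all 12 fully observed, P(fewer than 5 DLTs) from binomial(12, 0.60), (12, 0.45) and (12, 0.30) is 0.06, 0.30 and 0.72. P(at most 7 DLTs) is 0.56, 0.89 and 0.99. Rates set for finishing treatment therefore do not apply automatically to a 90-day window.

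**When could each window be read?** A 90-day window closes for patient 12 at 335 + 90 = day 425, about month 14. A 24-month window closes at 11 + 24 = month 35.

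**The case against.** **The sections can largely be reconciled.** The bracketed gloss in 9.1.1 supports 90 days for grade 3-4 GVHD. If 90 days covers every component, 2.1 and 9.2.4.1 agree for anyone treated past day 90. This stands for GVHD. The scope for the other components is still not stated, nor is early leaving settled.

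**The final count is safe from early leavers.** A reader might infer that they unsettle 14 of 26 as well. The documents do not support that: completion appears only in the stage-1 go rule, the final rule asks for DLT-free patients in all three places, and 9.1.1 makes anyone given any drug evaluable for toxicity.

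**The go rule may be usable.** It is tempting to say it can never be applied in time. That holds only if completion means 35 cycles, which no section says. Treatment is for up to 2 years, and 6.8.1 lets complete responders stop after at least 6 months.

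**The early decision is permitted, not required.** The word after sets an earliest point. Adverse events are reviewed every three weeks (2.1). Read plainly, the undated halt rule would let a later fifth DLT among the first 12 stop the trial. In the 90 days after patient 12 starts, 90/30.44 = 2.96, so 2 more patients enter at 1/month, or 3 at 1.2-1.3/month (90/25.4 = 3.5; 90/23.4 = 3.8). On that reading the harm is about 2-3 extra enrolments. This stands as a limit on the harm, but the plan does not say that the halt rule stays live after the decision.

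**Conclusion.** The concern holds. The primary outcome has no single stated time frame, and the plan permits its stage-1 safety decision before DLTs in the last patients could be seen. Both follow from the text without any assumption about onset.

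The size is illustrative. The rises from 0.06 to 0.17 (0.10-0.27 across onset patterns) and from 0.56 to 0.82 (0.70-0.93) need a decision at the earliest point, the whole 60% rate within 90 days, and even accrual at 1 patient/month; the central values also need uniform onset. The pairs belong to two different stage-1 rules. A reader might take 0.06 as the planned pass rate for an unsafe treatment, but that describes only the rule of fewer than 5 DLTs; section 9.2.4.1 designs on at least 5 DLT-free, where it is 0.56. The conflict between those rules is a separate problem. Nor do the documents show that the decision will be taken at month 11, only that nothing prevents it.

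**What to change.** 1. Reconcile sections 2.1, 8.2, 9.1.1, 9.1.3 and 9.2.4.1 to one DLT window for the primary outcome, and state which DLT components it covers. Of the stated windows, only 90 days can practically be evaluated at stage 1. Confirm, or justify afresh, that the 40% and 65% rates apply to the chosen window.
2. In 9.1.3 and 8.4.1, take the stage-1 decision only when each of the first 12 patients has had a DLT or completed that window. State whether enrolment pauses meanwhile, and whether later DLTs among the first 12 still halt the trial.
3. State how patients who leave before the end of the window without a DLT are counted.

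Cost: protocol and SAP wording, and a stage-1 decision up to about 90 days later (about month 14 instead of month 11 at 1 patient/month, for a 90-day window). If the 40% and 65% rates do not hold for the window, the cut-offs of 5 of 12 and 14 of 26 need new justification.

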9.2.4.2 STATISTICAL METHODS FOR EFFICACY ANALYSES

9.2.4.2.1 OVERALL RESPONSE RATE (ORR)

ORR will be summarized as a proportion. ORR will depend on the tumor type, and we will analyze for HL NHL, MDS, and AML individually, acknowledging that the numbers will be small. Descriptive statistics will be used to test the hypothesis that the ORR exceeds 10%.

9.2.4.2.2 DURATION OF RESPONSE (DOR)

DOR will be summarized using a Kaplan-Meier survival curve.

9.2.4.2.3 OVERALL SURVIVAL (OS)

OS will be summarized using a Kaplan-Meier survival curve.

10.0 LABELING, PACKAGING, STORAGE AND RETURN OF CLINICAL SUPPLIES

10.1 INVESTIGATIONAL PRODUCT

The investigator shall take responsibility for and shall take all steps to maintain appropriate records and ensure appropriate supply, storage, handling, distribution and usage of investigational product in accordance with the protocol and any applicable laws and regulations.

Clinical Supplies will be provided by Merck as summarized in **Table 13**.

Table 13. Product description

Product Name & Potency	Dosage Form
Pembrolizumab 50 mg	Lyophilized Powder for Injection
Pembrolizumab 100 mg/4mL	Solution for Injection

10.2 PACKAGING AND LABELING INFORMATION

Clinical supplies will be affixed with a clinical label in accordance with regulatory requirements. Subjects will receive open label pembrolizumab (MK-3475) vials.

10.3 CLINICAL SUPPLIES DISCLOSURE

This trial is open-label.

10.4 STORAGE AND HANDLING REQUIREMENTS

Clinical supplies must be stored in a secure, limited-access location under the storage conditions specified on the label. Receipt and dispensing of trial medication must be recorded by an authorized person at the trial site. Clinical supplies may not be used for any purpose other than that stated in the protocol.

10.5 DISCARD/DESTRUCTION/RETURNS AND RECONCILIATION

The investigator is responsible for keeping accurate records of the clinical supplies received from the sponsor, the amount dispensed to and returned by the subjects and the amount remaining at the conclusion of the trial. Where local discard and destruction is appropriate, the investigator is responsible for ensuring that a local discard/destruction procedure is documented.

11.0 ADMINISTRATIVE AND REGULATORY DETAILS

11.1 CONFIDENTIALITY

11.1.1 CONFIDENTIALITY OF DATA

All study records will be maintained in confidence, and such information will be divulged to the institutional review board, ethics review committee (IRB/ERC) or similar or expert committee; affiliated institution and employees, only under an appropriate understanding of confidentiality with such board or committee, affiliated institution and employees. Data generated by this trial will be considered confidential by the investigator, except to the extent that it is included in a publication as provided in the Publications section of this protocol.

11.1.2 CONFIDENTIALITY OF SUBJECT RECORDS

The study team, Merck, IRB/ERC, or regulatory authority representatives may consult and/or copy trial documents in order to verify worksheet/case report form data. By signing the consent form, the subject agrees to this process. If trial documents will be photocopied during the process of verifying worksheet/case report form information, the subject will be identified by unique code only; full names/initials will be masked prior to transmission to any party outside of the coordinating site. All subject data will be used and disclosed in connection with this trial in accordance with all applicable privacy laws, rules and regulations.

11.2 OBLIGATIONS OF SITE INVESTIGATOR

The Principal Investigator is responsible for the conduct of the clinical trial at the site in accordance with Title 21 of the Code of Federal Regulations and/or the Declaration of

Helsinki. The Study Site Principal Investigator is responsible for personally overseeing the treatment of all study patients. He/she must assure that all study site personnel, including sub-investigators and other study staff members, adhere to the study protocol and all FDA/GCP/NCI regulations and guidelines regarding clinical trials both during and after study completion.

The Principal Investigator will be responsible for assuring that all the required data will be collected and entered into the CRFs. Periodically, monitoring visits or audits will be conducted and he/she must provide access to original records to permit verification of proper entry of data.

11.3 AUDITING

The University of Chicago Comprehensive Cancer Center will perform routine Quality Assurance Audits of investigator-initiated clinical trials as described in the NCI-approved UC CCC DSM Plan. Audits provide assurance that trials are conducted and study data are collected, documented and reported in compliance with the protocol. Further, quality assurance audits ensure that study data are collected, documented and reported in compliance with Good Clinical Practices (GCP) Guidelines and regulatory requirements. The audit will review subjects enrolled at the University of Chicago in accordance with audit procedures specified in the UC CCC Data and Safety Monitoring plan.

A regulatory authority (e.g. FDA) may also wish to conduct an inspection of the study, during its conduct or even after its completion. If an inspection has been requested by a regulatory authority, the site investigator must immediately inform the University of Chicago Cancer Clinical Trials Office and Regulatory Manager that such a request has been made.

11.4 DATA MANAGEMENT

The investigator or qualified designee is responsible for recording and verifying the accuracy of subject data.

11.5 PUBLICATION

This trial is intended for publication, even if terminated prematurely. Publication may include any or all of the following: posting of a synopsis online, abstract and/or presentation at a scientific conference, or publication of a full manuscript.

12.0 APPENDICES

12.1 ECOG PERFORMANCE STATUS

Grade	Description
0	Normal activity. Fully active, able to carry on all pre-disease performance without restriction.
1	Symptoms, but ambulatory. Restricted in physically strenuous activity, but ambulatory and able to carry out work of a light or sedentary nature (e.g., light housework, office work).
2	In bed <50% of the time. Ambulatory and capable of all self-care, but unable to carry out any work activities. Up and about more than 50% of waking hours.
3	In bed >50% of the time. Capable of only limited self-care, confined to bed or chair more than 50% of waking hours.
4	100% bedridden. Completely disabled. Cannot carry on any self-care. Totally confined to bed or chair.
5	Dead.
* As published in Am. J. Clin. Oncol.: Oken, M.M., Creech, R.H., Tormey, D.C., Horton, J., Davis, T.E., McFadden, E.T., Carbone, P.P.: Toxicity And Response Criteria Of The Eastern Cooperative Oncology Group. Am J Clin Oncol 5:649-655, 1982. The Eastern Cooperative Oncology Group, Robert Comis M.D., Group Chair.	

